**Aim 2: Examine the mediators underlying the expected change in opioid use during treatment.**

To accomplish Aim 2, we will use PROCESS bootstrap mediation models to evaluate the extent to which early treatment changes in the primary mechanisms (pain intensity and emotional distress, i.e., depression and anxiety) will predict subsequent late-treatment changes in opioid use (primary outcome), and the extent to which these associations are shared across the three treatments, or if some are unique to one or a subset of treatments.

**Hypothesis 2a:** If changes in pain intensity and emotional distress are mechanisms shared by CT, MM, and AS, then changes in opioid use in all three treatments will be predicted to approximately the same extent by changes in the primary mechanisms.

**Hypothesis 2b:** If changes in the primary mechanisms are *specific* to one (or a subset) of the three treatments, then Treatment Group X Assessment Period interactions will reveal that late-treatment changes in opioid use will be substantially and uniquely predicted by early-treatment changes in the primary mechanism(s) in one (or a subset) of the three conditions only.

We also predict that change in the mechanism variables will precede and predict change in outcome, but not vice versa.

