in pain intensity when assigned to MBCT ( $r = -.36$ ; within condition effect), with the boundary of significance identified as a Pain Catastrophizing Scale score of  $\leq 16.35$ ; (2) a further interaction effect for MM vs. MBCT ( $b = -.23$ ,  $p = .05$ , CI:  $-.46$  to  $.003$ ), showing that higher baseline mindfulness was associated with greater improvement in pain intensity in MBCT ( $r = .40$ ; within condition effect), with the boundary of significance identified as a Five Facet Mindfulness Questionnaire Observe Scale score of  $> 15.03$ . Thus, based on these effects in our pilot work testing the LA&E predictions, we anticipate that the proposed sample size for this supplemental project of  $N=90$  will be sufficient to detect medium to large effects (at the  $\alpha < .05$  level). Hypotheses 1a-1c would be supported if an interaction effect emerges (significant at the  $\alpha < .05$  level) and one or more of the within group effect sizes (of the moderator on the primary outcome) are medium or large.

*For Aim 2 of this supplemental study*, the primary mediator measures are: (1) a Numerical Rating Scale assessing characteristic pain intensity (in the past week); (2) the PROMIS Depression scale; and (3) the PROMIS Anxiety scale. Additional secondary mediators, selected per the primary mechanisms examined in the parent study (e.g., catastrophizing, mindfulness, activity level), will also be explored in the supplemental project sub-sample. The association between treatment-related changes in the primary mechanisms on changes in outcome will be tested via three PROCESS tests with 5,000 bias-corrected bootstrap resamples. The PROCESS bias-corrected bootstrap approach has been shown to consistently be the most powerful test of mediation (i.e., compared to the Sobel test, Baron and Kenny's approach) and is appropriate for small sample sizes. We will examine the significance of each path to determine if treatment condition has a differential effect on the mediator and/or outcome (although treatment-related differences in outcome are not expected), and whether early change in the mechanism is associated with later change in outcome. In the instance of a possible specific vs. shared mechanism effect, post-hoc associations will be tested via correlations to identify estimates of effect sizes for descriptive purposes.

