We applied this approach to the three active treatments in pilot data obtained in our RCT comparing CT, Hypnosis and Hypnotic-CT (within the subsample of participants who reported musculoskeletal pain who were prescribed opioids,  $N=18$ ) to examine the relative statistical power achieved in that sample to detect medium to large effects for the analyses planned for this supplemental project. In two PROCESS models testing if early change in pain intensity or depression were specific vs. shared mechanisms in accounting for late treatment change in opioid use, results showed: (1) a non-significant effect of condition on outcome (path *c*) as well as on both mechanisms (path *a*); and (2) a significant effect of both mechanisms on the outcome (path *b*;  $ps < .01$ ). Post-hoc correlations were then conducted for descriptive purposes. We found that early change in both pain intensity and depression were significantly associated with later change in opioid use across groups ( $rs = .58$  and  $.68$ , respectively); on the other hand, early change in outcome was not significantly associated with later change in mechanism. Taken together, these results (1) provide support for early change in pain intensity and depression as underlying later reductions in opioid use, and (2) are consistent with a shared mechanisms account for the role of early change in pain intensity and depression as mechanisms driving decreased opioid use across the treatments studied in this pilot data. The proposed sample size and procedures of the supplemental project will afford the capacity to test these associations more definitively.

Overall, our pilot data indicate that if changes in outcome and mechanisms in the supplemental project are medium to large in nature, then the sample size of  $N=90$  will be adequate to test the mediation hypotheses 2a and 2b. Support for Hypothesis 2a and the shared mechanisms conceptualization would be found in the instance of a non-significant effect

of condition on the mechanism variable, but significant ( $\alpha \leq .05$ ) effect of the mechanism on outcome collapsed across groups. Support for Hypothesis 2b on the other hand would be found in the instance of a significant effect of condition on the mechanism, with change in the mechanism differentially associated with change in outcome across treatment conditions.

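### The Aim 2 support rules define shared and specific mechanisms inconsistently; read as written in D6s, they give no verdict when arms differ on the mechanism but the mechanism predicts opioid change alike in every arm

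*Protocol*

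**What the plan says.** Call the effect of condition on early mechanism change path a, and the effect of that change on later opioid change path b.

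- **D6s, rule for 2a.** The rule opens: "Support for Hypothesis 2a and the shared mechanisms conceptualization would be found in the instance of a non-significant effect"; the effect meant here is path a. It also asks for a significant "effect of the mechanism on outcome collapsed across groups". Path a must be null and pooled path b must be present.
- **D6s, rule for 2b.** The rule opens: "Support for Hypothesis 2b on the other hand would be found in the instance of a significant effect of condition on the mechanism". A second clause then sets a condition on the slopes: "with change in the mechanism differentially associated with change in outcome across treatment conditions". Path a must be present and path b must differ by arm.
- **D6s, what is read from the models.** Three PROCESS models with 5,000 bias-corrected resamples are planned. Then: "We will examine the significance of each path to determine if treatment condition has a differential effect on the mediator and/or outcome". Where a specific or shared effect looks possible, correlations follow for description only.
- **A2a (and the Précis), Hypothesis 2a.** If the mechanisms are shared, "changes in opioid use in all three treatments will be predicted to approximately the same extent by changes in the primary mechanisms". Nothing is said about path a.
- **A2b, Exploratory Hypotheses 3a and 3b.** These carry the same two models into the post-treatment weeks. 3a ties shared to small, non-significant condition effects on the mechanism. 3b ties specific to a group by period interaction and a significant mechanism-outcome association, and does not say that slopes differ between arms.
- **SAP.** It covers dose-change proportions and ANOVA of secondary outcomes. It has no mediation analysis and no Aim 2 rule.

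**The concern.** Arms differing on a mediator that acts with a common slope is the ordinary mediation result, and it is what a relative indirect effect (a × b) estimates. The D6s rules have no place for it: 2a fails because path a is significant, and 2b fails because the slopes are equal.

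The sections also disagree on how to label it. It is shared under A2a, neither under D6s, and arguably specific under 3b. Aim 2 carries primary hypotheses, so the conclusion for the same data would depend on which section the analyst follows. The bootstrap, which D6s justifies as the most powerful test of mediation, would not settle the matter, because no rule refers to its interval.

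**Working it through.** **1. The rules side by side**

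| Path a | Path b | D6s | A2a wording |
|---|---|---|---|
| not significant | common, significant | 2a | 2a |
| significant | differs by arm | 2b | 2b |
| significant | common, significant | neither | 2a |

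The third row follows from the wording and needs no simulation.

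**2. The plan's own figure.** D6s says N = 90 "will be adequate to test the mediation hypotheses 2a and 2b" if effects are medium to large. No power or numerical effect size is given, so this cannot be reproduced. The completer count can: 90 × 0.80 = 72.

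**3. Inputs for sizing the gap**

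- From the protocol: N = 90 randomised, 72 with complete data, three arms, α = .05.
- Assumed: equal arms; two-sided tests; path a of f = .25 (medium) or .40 (large); common within-arm path b of r = .3 to .5; one arm raised on the mechanism; no direct effect of condition on outcome.
- Also assumed: 2b's slope clause is tested by a 2-df arm by mechanism-change F test at .05. The protocol names no test for that clause.

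**4. Formula.** With equal slopes the interaction test rejects 5% of the time whatever path a does. Therefore

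P(no verdict) = power(a) × 0.95 + P(a not significant and b not significant).

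Power for path a comes from the noncentral F distribution:

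| N | f | power(a) | first term |
|---|---|---|---|
| 72 | .25 | .443 | .443 × .95 = .42 |
| 90 | .25 | .540 | .540 × .95 = .51 |
| 72 | .40 | .853 | .853 × .95 = .81 |
| 90 | .40 | .926 | .926 × .95 = .88 |

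The second term is at most .003 at r = .5. At r = .3 it reaches about .15 (N = 72, f = .25).

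**5. Simulated totals, r = .3 to .5, F-test reading**

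| N | f = .25 | f = .40 |
|---|---|---|
| 72 | 43–56% | 81–86% |
| 90 | 52–59% | 88–90% |

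Repeat runs move the ends by a point or two. Most of the remaining trials are called 2a, because path a was missed. With a small path a (f = .10), 2a is the usual result (65–90%) and no verdict occurs in 10–35%; those two ranges also include r = .68.

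**6. Same truth, other readings of 2b**

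- Within-arm correlation significant in some but not all arms: no verdict in 18–35% (N = 72) and 25–53% (N = 90). The difference is made up by 2b calls, although the true slopes are equal.
- 3b wording (path a and pooled path b both significant): no verdict in 0–28%.

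**7. Indirect effect against verdict** (r = .50, F-test reading, 400 trials, 1,000 bias-corrected resamples). At N = 90 at least one relative indirect-effect interval excludes zero in 76% of trials at f = .25 and 97% at f = .40. Of those trials, 71% and 91% get no verdict. At N = 72 the intervals exclude zero in 69% and 94%, and 59% and 85% of those get no verdict.

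**The case against.** The strongest reply has four parts.

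- **A null path a belongs to the authors' idea of shared.** 3a repeats it, so A2a may be the loose wording and D6s the intended one. 3b, read literally, could take the omitted pattern as specific. This stands in part: the defect is disagreement between sections, not a result that no section could classify. But 3a and 3b are exploratory, and D6s, the only place with decision rules for the primary hypotheses, adds the unequal-slope condition.
- **The high percentages depend on a test that the protocol does not state.** This stands. They are conditional on the F test, and other readings give lower rates.
- **The pattern may not arise.** The pilot found no significant path a, and the protocol expects no differences between arms in outcome. The pilot had N = 18, and the expectation concerns outcome, not the mechanism. 2b itself requires a condition effect on the mechanism.
- **Nothing is hidden.** D6s examines every path, so the pattern would be visible in the results. This stands: what is missing is a stated conclusion, not the data.

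A reader might infer that a real indirect effect of this kind usually gets no verdict. The documents do not support that as a general statement. It needs both the F-test reading and a path a that is at least medium. At N = 72 with f = .25 and r = .5, 2a is the more frequent result.

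**Conclusion.** The concern holds as an inconsistency with a definite gap. A2a, A2b and D6s define shared and specific differently. Under D6s as written, a significant path a with a common path b supports neither hypothesis, and the bootstrap indirect effect decides nothing. This part rests on wording alone.

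The size is conditional. Under the F-test reading, no verdict occurs in about 43–59% of trials with a medium path a and 81–90% with a large one, at N = 72 to 90. Under the other two readings it is 0–53%. The values of f and r are assumptions, because the protocol says only medium to large. The spread between readings is a reason to name the test. The point should be corrected, but it does not invalidate the Aim 2 data.

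**What to change.** 1. Reconcile the Précis, A2a, A2b and D6s so that 2a, 2b, 3a and 3b use one definition each of shared and specific, and add the Aim 2 analysis to the SAP.
2. Name the arm by mechanism-change interaction as the test for 2b's slope clause.
3. Ask two questions separately. *Is the slope common?* Report the interaction and the arm-specific slopes with confidence intervals, and do not take a non-significant interaction as proof of equal slopes. *Is the mechanism engaged more in one arm?* Report path a.
4. Report the relative indirect effects with bootstrap intervals, and add a third stated outcome: the mechanism acts similarly across treatments and is engaged more by one of them.

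The cost is one interaction term per model, more intervals over three mediators (which need a multiplicity statement), and revised wording. The SAP is dated July 2024 and written in the past tense, so the change must be dated, and labelled post hoc if results have been seen.

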## HUMAN PARTICIPANTS SECTION

### **E. Risk to Participants**

#### **E1. Human Participants Involvement and Characteristics**

We plan to enroll up to 90 participants into the study. Our primary source of potential participants for this study is all individuals who have been seen as patients at either Harborview Medical Center (HMC) or the University of Washington Medical Center (UWMC), and who meet study eligibility criteria.

If needed and required, we will also recruit from other modalities. These other modalities include through flyers/brochures/advertisements in various clinics and hospital spaces, the UW Medicine Newsroom, clinician and participant referrals, social media/online recruitment, and nationally, if needed.

#### **E2. Sources of Materials**

Several sources of information will serve as data for the study, including medical record reviews, self-report assessments and interviews, ActiGraph activity data, and audio-recorded treatment sessions (to be used for supervision and determination of adherence and fidelity). The study design involves non-invasive procedures.

The data described will be collected solely for research purposes.

### **E3. Potential Risks**

It is anticipated that participants, irrespective of treatment condition, will experience significantly more benefits than risks from participation in this study. Although the methods and interventions have limited participant risks, several safeguards will be implemented to reduce these.

#### **E3a. General / Reaction to Assessments**

Regarding research risks, participants may experience fatigue and/or boredom while completing the telephone/online assessments, EMA surveys, and/or the treatment sessions. Some participants may also experience mild anxiety, frustration, and/or stress while answering sensitive questions about depression, pain, and mood. As a result of answering questions about pain, some participants may focus more on their pain, which may lead to a temporary increase in pain intensity. Participants will be told that such phenomena associated with close self-monitoring are a part of the treatment approaches we are offering, and will be addressed as part of the interventions.

#### **E3b. Stress / Discomfort Caused by Treatments**

Our research team has had a great deal of experience with each of the treatments to be examined in this study, and each has minimal risks. The three types of treatment involve discussions about pain and related topics in a group setting that may make some individuals feel uncomfortable. Some participants may also experience mild anxiety, frustration, and/or

stress during the course of treatment should any topics or activities prove difficult for them. Some individuals learning cognitive restructuring of thoughts and beliefs or practicing mindfulness meditation may remember past experiences that are uncomfortable and/or cause distress, even after the session has ended. Regarding the mindfulness meditation training, some individuals may find the state of focused awareness uncomfortable, or may experience mild disorientation or grogginess during or after the session has ended due to the occasionally relaxing nature of this practice. Regarding the activation skills intervention, although clinicians will instruct participants engage only in safe and personally appropriate activities, there is a risk that participants may experience physical strain or injury when conducting activities with a physical component.

Should any participants experience these discomforts, the intervention leaders are clinicians with the expertise and clinical privileges needed to address these in appropriate clinical fashion in real time. Study investigators (Drs. [name], [name], and [name]) are also available on site for additional consultation or support if needed. There is little chance of physical injury from the treatment procedures described above.

One potential risk is that participants may experience some distress when sharing personal information during the group telehealth intervention, although this is a relatively low risk event, because personal disclosure will not be specifically elicited. To reduce distress about public disclosure, the meaning of confidentiality will be explained at the outset of each session and group members will be asked to maintain the confidentiality of all session content. Participants will be explicitly instructed that revealing deeply personal information, by exploring the past or confiding in the group about personal information, is not considered part of the treatment protocol. Additionally, any participant expressing significant discomfort in the group treatment will be referred for alternative treatments. Participants may also feel uncomfortable because the sessions will be audio-recorded. Participants who choose to participate in the intervention will be advised at the time of informed consent that sessions will be audio recorded, so that they may self-select out of the study if recording is a barrier. Participants will be informed that the session recordings will be used only for treatment implementation monitoring and training purposes, and that no one outside the study staff will have access to the recordings.

### **E3c. Actigraphy Device**

Participants may find it uncomfortable or inconvenient in general to wear a device like an ActiGraph both during the day and while sleeping. There is no risk of electrical shock while wearing the ActiGraph and it cannot track where participants are, record any verbal/audio, or track what behavior they are specifically doing. Participants may experience sweating or skin irritation while wearing the ActiGraph if they have sensitive skin.

### **E3d. Privacy and Confidentiality**

Participants may also worry about the confidentiality of their responses during the assessments. There is a risk of invasion of privacy in that the research staff directly involved with data collection will need to keep participants' names, addresses (email and postal), and phone numbers for the duration of the study in order to contact them for the follow-up assessments. There is also a chance that a participant's identity and participation in the study may be discovered by an outside party given the group intervention dynamic. Given that this is a group intervention, participants within each group will know the first names and some information about other participants. However, participants will be encouraged to share only

their first names, and to disclose only that information that they are comfortable sharing and that pertains to pain and treatment.

### **E3e. Mental Health Issues / Suicidality**

Although unlikely, it is possible that by participating in the study it may be discovered that a participant is suicidal or experiencing significant mental health issues. Please note that these conditions would also likely be detected in the course of usual care. The study suicide protocol will be implemented in the instance of a participant expressing suicidality.

## **E4. Protection Against Risk**

### **E4a. General / Reaction to Assessments**

Participants will be informed during the consent process and throughout the study they do not have to discuss any topics they do not wish to during treatment or the assessment periods. In addition, participants will be informed in the consent process they are free to stop any session, treatment, or assessment at any time. Participants are informed they may refuse to answer any questions that make them feel uncomfortable.

All study personnel who conduct the assessments will be qualified, trained, and closely supervised by study investigators. All participants will be clearly informed of their right to withdraw from the study at any point without adversely impacting their routine medical, psychiatric, or psychotherapeutic care.

All participants will be offered the opportunity to discuss any situations or experiences associated with the study procedures that they deem uncomfortable or adverse with the UW Co-PI, [name], who is a licensed clinical psychologist. [name] is a trained psychologist who has experience assessing the level of distress of patients and proceeding accordingly whenever an adverse event should arise.

### **E4b. Stress / Discomfort Caused by Treatments**

Researchers will take multiple steps to ensure and monitor the well-being of participants during treatment. Study investigators, led by [name], will offer ongoing, scheduled supervision and consultation with study clinicians, including routine assessment of any potential problems or adverse events.

For all treatment interventions, several steps will be taken to monitor the possibility of adverse events participants may experience as a result of the treatment interventions. First, during the recruitment process, research staff will clearly outline the physical components of the activation skills intervention. In doing so, staff will also instruct individuals who are concerned about the physical nature of the intervention to consult their physician before agreeing to participate. Additionally, staff will clearly outline the possible risks of discomfort and distress when changing thoughts and beliefs as it relates to the cognitive therapy intervention, as well as possible mild disorientation and grogginess as it relates to the mindfulness meditation intervention.

Second, clinicians will employ several protective measures when administering the treatment interventions. As it relates to the activation skills intervention, at the first treatment session clinicians will get to know the personal physical capabilities of each participant, allowing any future physical activity recommendations to be tailored to the individual. Further, before participants complete any assigned physical activities, the clinician will review the activity with the participant to ensure that it is reasonable and safe. Lastly, the clinician will routinely assess during the treatment phase whether participants are experiencing any adverse effects related to the activity skills intervention, and will (in conjunction with the study medical doctor, if needed) advise the participant whether they should stop or modify their activity, or recommend they seek guidance from their primary health care provider (if the event is significant but non-imminent) or urgent/emergency care (if the event is life-threatening or an urgent, acute medical issue). As it relates to the cognitive therapy and mindfulness meditation interventions, during each treatment session clinicians will routinely assess whether participants are experiencing any adverse effects related to the treatment interventions, and will (in conjunction with PI supervision, if needed) advise the participant whether they should stop or modify participation in mindfulness meditation or cognitive therapy treatment activities.

